
Role of this analysis plan

To better understand the mechanism of action of TMS, and of any putative benefit of cgitBS over standard repetitive TMS, we will examine a set of hypotheses derived from prior literature. Here, we describe the spectroscopic processing and statistical analysis plan.

The main study rationale is to assess whether clinical response to treatment is associated with GABA changes in the DLPFC.

Definitions of measures

- *Clinical improvement*
Mean change in depression measure from baseline (17-item HDRS total score as primary measure); changes from baseline in BDI, QIDS-SR-16, PHQ-9 and GAD-7 will be used for exploratory analyses only)
- *Treatment response*
Reduction in depression measure (17-item HDRS total score) of 50% or greater compared to baseline
- *Metabolite ratios*

GABA levels relative to Cr (GABA+/Cr), Glx levels relative to Cr (Glx/Cr) and GABA levels relative to Glx (GABA+/Glx as no macromolecule suppression). Glx and Cr will be estimated from non-edited spectra.

Primary hypotheses

1. Changes in depression symptoms on 17-item HDRS (16 weeks versus baseline) will be associated with change in GABA+/Cr between baseline and 16 weeks (post minus pre-treatment) in both treatment groups with increase in GABA+/Cr expected to be associated with decrease of HDRS (improvement).
2. Changes in depression symptoms on 17-item HDRS (26 weeks versus baseline) will be associated with change in GABA+/Cr between baseline and 16 weeks (post minus pre-treatment) in both treatment groups with increase in GABA+/Cr expected to be associated with decrease of HDRS (improvement).
3. Greater clinical improvement on 17-item HDRS (16 and 26-week vs baseline) will be associated with lower GABA+/Cr at baseline across both treatment groups.

Secondary hypotheses

1. GABA+/Cr will be increased after treatment compared to baseline for treatment responders across both treatment groups (a) and (b) GABA+/Cr increase will be higher in responders than in non-responders.
2. GABA+/Cr increase will be higher in cgtTBS compared to rTMS group (all patients).
3. Greater averaged and sustained clinical improvement on 17-item HDRS (averaged over 8,16 26-week follow-up) will be associated with more GABA+/Cr change across both treatment groups.
4. Greater averaged and sustained clinical improvement on 17-item HDRS (averaged over 8, 16 26-week follow-up) will be associated with lower GABA+/Cr at baseline across both treatment groups.

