5. Glx/Cr will be increased after treatment compared to baseline for treatment responders across both treatment groups (a), and Glx/Cr increase will be higher in responders than in non-responders (b).
6. Glx/Cr increase will be higher in cgtTBS compared to rTMS group (all patients).
7. Changes in depression symptoms on 17-item HDRS (16 weeks versus baseline, and 26 weeks versus baseline) will be associated with change in Glx/Cr between baseline and 16 weeks (post minus pre-treatment) in both treatment groups.

Exploratory hypotheses:

1. All the above hypotheses will be tested with other measures of depression used in the study to test robustness of findings, namely HDRS-6, BDI, PHQ-9 and QIDS-SR-16
2. GABA+/Glx changes will be associated with clinical outcomes (17-item HDRS at 16 and 26 weeks).
3. GABA+/Cr and Glx/Cr changes correlate with rAI-DLPFC net outflow changes (16 weeks vs baseline).
4. GABA+/Glx is associated with rAI-DLPFC FC and net outflow (baseline and 16 weeks) with stronger association in treatment responders after treatment compared to baseline.

5. Clinical subtypes, especially TRD severity and comorbid anxiety are associated with changes in GABA+/Cr.
6. Treatment response is associated with changes in the association between intrinsic within and between brain network FC metrics and DLPFC GABA+/Cr, Glx/Cr and GABA+/Glx levels.

Required data

- MEGA-PRESS MRS and resting-state functional MRI at baseline and, where available, at 16 weeks
- Treatment group assignment (rTMS or cgtTBS)
- Participant age, sex, and study centre and MRS protocol/platform
- For each participant, whether protocol deviations were submitted on the basis of stimulation sequence or localisation method received
- For each participant, whether there were any changes in medications in BNF Chapter 4 between baseline and 16 weeks (including starting and stopping medications)
- For each participant, whether ECT was delivered between baseline and 16 weeks
- For each participant, whether they started psychotherapy between baseline and 16 weeks
- For each participant, whether any major protocol deviations occurred from baseline to 16 weeks
- 17-item HDRS total score at baseline, 8-week follow-up, 16-week follow-up and 26-week follow-up.
- 6-item HDRS total score at baseline, 8-week follow-up, 16-week follow-up and 26-week follow-up.
- Beck Depression Inventory at baseline, 8-week follow-up, 16-week follow-up and 26-week follow-up

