- 16-item self-report Quick Inventory of Depression Symptoms (QIDS-SR-16) at baseline, 8-week follow-up, 16-week follow-up and 26-week follow-up
- 9-item Personal Health Questionnaire (PHQ-9) at baseline, 8-week follow-up, 16-week follow-up and 26-week follow-up
- Total score on the GAD-7 measure of anxiety
- Massachusetts Treatment Resistance category (mild, moderate, severe as defined in trial protocol)

Regions of interest (ROIs) / Voxel of interest (VOI)

- For MRS, a voxel (20x45x30mm) was placed on the left DLPFC based on the individual T1 anatomical image acquired prior to the MRS session.
- Grey Matter (GM), White Matter (WM) and Cerebrospinal fluid (CSF) will be parcellated through GANNET segmentation with SPM12. The GM values will be covariates of no interest in the statistical analysis.

Sensitivity analyses

In order to examine whether quality of MRS affected the results, we will conduct sensitivity analyses to

- assess a potential effect from outliers in voxel position. For this, coverage of anatomical DLPFC (in percent) and overlap with TMS brain target within the individual MRS voxels will inform through the sensitivity analysis.
- assess spectral fitting quality effects. For this, only data with higher quality data fit will be used to repeat primary and secondary hypothesis with $p < 0.1$ results.

Statistical tests

Primary Hypotheses

- The correlation between change in GABA+/Cr between baseline and 16 weeks (post minus pre-treatment) and clinical improvement will be tested by regression with the following covariates for P1 and P2:
 - *Age*
 - *Sex*
 - *Treatment group (rTMS or cgtTMS)*
 - *MGH treatment resistance*
 - *Baseline 17-item HDRS*
 - *Study centre*
 - *MRS platform (scanner/protocol)*
 - *MRS quality (GABA+ fitting error)*

$P < 0.01666$ will be the level considered for statistical significance ($p < 0.05/3$, i.e. 5% significance level with Bonferroni correction for 3 co-primary hypotheses). For missing data (e.g. due to poor spectra quality, participants' absence for the scanning or incompleteness of whole MRS sessions) we will take an available data approach, meaning individuals with enough data for a model will be included in that model's analysis.

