- For P3, a mixed effects model will be used with participant as random effect to account for three repeated measures. Each participant will contribute up to 3 repeated outcome measures to the model in addition to the baseline HDRS-17 score. The model will be adjusted for the stratification and minimisation variables: baseline HDRS-17 score, baseline Massachusetts General Hospital Treatment Resistant Depression score, and study centre as part of the covariable detailed above. For missing data, we will take an available data approach, meaning individuals with enough data for a model will be included that model's analysis.

Secondary Hypotheses

Secondary hypotheses S2, S3, S5, S6, S7 will be analysed as above, for S1 and S4 we will use a mixed model

- A Linear mixed model will be used with GABA+/Cr as the dependent variables.
- Independent variables will be the *Treatment* response group, *Time* (pre-and post) and *Treatment type*
- Covariates of no interest include
 - *Age*
 - *Sex*
 - *MGH treatment resistance group*
 - *Study centre*
 - *MRS platform (scanner/protocol)*
 - *MRS quality (GABA+/Glx fitting error respectively)*

We will take an available data approach, meaning individuals with enough data for a model will be included in that model's analysis. For secondary analyses $P < 0.05$ will be considered significant without Bonferroni correction.

The statistical analysis for primary and secondary hypotheses will be performed using a current version of either SPSS, SAS, Stata or R (for graphical illustrations). Diagnostic plots of model residuals, and the results of the Shapiro-Wilk test, will be used to determine whether variable transformations are required.

Exploratory hypotheses

Exploratory tests will be undertaken using current versions of either established advanced image analyses, SPSS, SAS, Stata or R (for graphical illustrations).

Included participants

All trial participants with baseline T1-weighted structural MRI, and MRS passing quality control criteria as detailed later in this document. We will include only participants that received the treatment to which they were assigned (that is, participants without protocol deviations on the basis of stimulation sequence or localisation method used).

Data processing

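### P2 drops scanned participants who lack a week-26 HDRS-17 even when weeks 8 and 16 were rated; a repeated-measures model would keep them

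*SAP*

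**What the plan says.** The Primary hypotheses section defines P1 at one visit: "Changes in depression symptoms on 17-item HDRS (16 weeks versus baseline) will be associated with change in GABA+/Cr between baseline and 16 weeks". P2 is defined at another: "Changes in depression symptoms on 17-item HDRS (26 weeks versus baseline) will be associated with change in GABA+/Cr between baseline and 16 weeks". The predictor is the same in both, and only the HDRS-17 visit differs.

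Under Statistical tests, Primary Hypotheses, the method for both is: "The correlation between change in GABA+/Cr between baseline and 16 weeks (post minus pre-treatment) and clinical improvement will be tested by regression". The covariate list that follows includes baseline HDRS-17 but no post-baseline score. Each hypothesis counts as one of three co-primaries at 0.05/3.

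For missing data, "we will take an available data approach, meaning individuals with enough data for a model will be included in that" particular model's analysis. The examples of missingness concern spectroscopy only, such as poor spectra and "absence for the scanning or incompleteness of whole MRS sessions". A missing follow-up HDRS-17 is not mentioned.

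For P3 the plan uses a mixed model: "Each participant will contribute up to 3 repeated outcome measures to the model in addition to the baseline HDRS-17 score". Required data already lists "17-item HDRS total score at baseline, 8-week follow-up, 16-week follow-up and 26-week follow-up". The Sensitivity analyses section covers voxel position and spectral fit quality, not lost ratings.

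**The concern.** The SAP does not call the P1 and P2 regressions separate. Two single-visit outcomes, a regression, and inclusion decided model by model leave no other natural reading. Someone scanned twice and rated at weeks 8 and 16, but not at week 26, does not have enough data for P2 and is left out. Those two ratings carry information about the missing one, and the regression does not use it.

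There are two consequences. Whenever week-26 ratings are missing, P2 loses precision that could partly be recovered, at a threshold already reduced for three co-primaries. If participants who are still depressed at week 16 are also less likely to be rated at week 26, P2 selects on a correlate of its own outcome, and the GABA slope moves towards zero.

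The point concerns missing HDRS-17 in people who have both scans. It does not concern missing scans, which no HDRS model can repair.

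**Working it through.** **The plan's own figure.** 0.05/3 = 0.016667, which agrees with the stated 0.01666. The two-sided critical value is 2.394. The SAP states no sample size, power, effect size or attrition to reproduce.

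**Assumed inputs (none from the SAP).** 100 participants with both scans; true standardised slope of HDRS-17 on GABA+/Cr change -0.35 at each visit; slope on baseline HDRS-17 0.3; residual correlations 0.7 (weeks 8 and 16), 0.7 (weeks 16 and 26) and 0.6 (weeks 8 and 26); 10 to 30% of week-26 ratings missing.

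**Random loss.** Let m be the fraction missing at week 26, and R² the squared multiple correlation of the week-26 residual on the week-8 and week-16 residuals.

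R² = (0.7² + 0.6² - 2 × 0.7 × 0.6 × 0.7) / (1 - 0.7²) = 0.262/0.51 = 0.514

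Relative to no missing data, the large-sample slope variance is 1/(1 - m) for the single-visit regression and 1 + [m/(1 - m)](1 - R²) for the joint model.

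| m | Single-visit | Joint | Ratio |
|---|---|---|---|
| 0.2 | 1.250 | 1 + 0.250 × 0.486 = 1.122 | 1.11 |
| 0.3 | 1.429 | 1 + 0.429 × 0.486 = 1.208 | 1.18 |

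Simulation agrees. At 20% random loss the standard errors were 0.102 and 0.096, and (0.102/0.096)² = 1.13. At 30% the joint variance was about 16% lower, and 1/0.84 = 1.19. Neither estimate is biased.

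**Loss related to week-16 HDRS-17.** The chance of a missing week-26 score follows a logistic rule in the week-16 score, with worse patients lost more often. At 20% missing (up to 4,000 simulated trials per cell):

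| Odds ratio per SD | Single-visit slope (SE) | Joint slope (SE) | Attenuation of single-visit slope |
|---|---|---|---|
| 1.5 | -0.344 | not recorded | 1 - 0.344/0.350 = 1.7% |
| 2.5 | -0.331 (0.099) | -0.350 (0.096) | 1 - 0.331/0.350 = 5.4% |
| 4 | -0.316 (0.100) | -0.349 (0.098) | 1 - 0.316/0.350 = 9.7% |

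Across odds ratios 2.5 to 4, the single-visit slope is -0.339 to -0.327 with 10% missing and -0.327 to -0.310 with 30% missing.

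Power at 0.0167, by Φ(|slope|/SE - 2.394), with 20% missing:
- single-visit: 0.331/0.099 - 2.394 = 0.95, or 83%; 0.316/0.100 - 2.394 = 0.77, or 78%;
- joint: 0.350/0.096 - 2.394 = 1.25, or 89%; 0.349/0.098 - 2.394 = 1.17, or 88%.

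**A second design.** With true slope -0.30, no covariates and n = 100, 20% missing at log-odds 1 or 2 per SD of week-16 change gave single-visit slopes of -0.276 and -0.251, against -0.297 and -0.298 jointly. The second is a severe rule, an odds ratio of about 7.4. When loss depended only on GABA change, the single-visit slope was unbiased.

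**The case against.** A baseline-adjusted regression at week 26 is a legitimate answer to a week-26 hypothesis, and the SAP states its estimator, covariates, threshold and missing-data rule. P3 concerns more than one visit, so its mixed model does not contradict P2. This stands: the point is a better method on data already collected, not an internal inconsistency.

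The bias is conditional and often small. Odds ratios of 2.5 to 4 per SD imply about 6-fold (2.5²) to 16-fold (4²) odds of loss between patients one SD above and one SD below the mean. Even then the shift at 20% missing is 0.019/0.099 = 0.19 to 0.034/0.100 = 0.34 of a standard error. This also stands, and it limits the weight of the point.

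Two stronger readings are tempting. One is that P1 suffers equally. Its outcome and the second scan both fall at week 16, so anyone with a GABA+/Cr change was seen around then, and loss of that rating is probably small (an inference, as the SAP gives no counts). The other is that attrition will make a lasting GABA association appear to fade. The SAP nowhere plans to read a significant P1 with a non-significant P2 in that way. In simulation (n = 100, 20% missing) that pattern arose in about 12% of trials under purely random loss, 15 to 17% at odds ratios 2.5 to 4, and still about 7% under the joint model. Much of it is ordinary imprecision.

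S3, on improvement averaged over weeks 8, 16 and 26, bears on sustained association. It is secondary and does not repair P2.

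**Conclusion.** The point holds for P2. Loss of participants and of precision is certain if any scanned participant lacks a week-26 rating. At 20 to 30% random loss the slope variance is roughly 10 to 20% larger than it need be, given residual correlations of 0.6 to 0.7. Attenuation occurs only if loss is related to the course of HDRS-17. With 20% missing it is negligible under mild dependence and reaches about 10% only under strong dependence; harsher rules would give more. All these sizes are illustrations. The documents do not support a claim that P2 is invalid, that P1 is materially affected, or that the plan will misread discordant results. The change is worth making because the data are already requested and the plan already uses repeated HDRS-17 scores in P3.

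**What to change.** Fit one repeated-measures model of HDRS-17 at weeks 8, 16 and 26 in all participants with both scans who otherwise qualify. Include visit, GABA+/Cr change by visit, baseline HDRS-17 by visit, the covariates already listed, and an unstructured within-person covariance. Take P2 as the GABA-change slope at week 26 and, for consistency, P1 as the slope at week 16, each tested at 0.0167 as now. Because baseline HDRS-17 by visit is in the model, the GABA slope is the same whether the outcome is the score or its change.

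Keep the two single-visit regressions as sensitivity analyses. If persistence or fading is discussed, report the week-26 minus week-16 slope difference with its confidence interval.

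The cost is a few sentences in the SAP and a slightly larger model, with no new participants or measurements. The model still assumes that ratings are missing at random given the observed HDRS-17 scores and the model's covariates. It remains exposed to loss driven by the unobserved week-26 state, and it does not help participants without a second scan.

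### P1 and P2 test a GABA+/Cr change score without a supportive model for baseline GABA+/Cr, so a true P3 could make them look like evidence of a change mechanism

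*SAP*

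**What the plan says.** Under Primary hypotheses, P1 and P2 relate HDRS-17 change (to 16 and to 26 weeks) to GABA+/Cr change from baseline to 16 weeks, with "increase in GABA+/Cr expected to be associated with decrease of HDRS (improvement"). P3 reads: "Greater clinical improvement on 17-item HDRS (16 and 26-week vs baseline) will be associated with lower GABA+/Cr at baseline across both treatment groups".

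Under Statistical tests, Primary Hypotheses, the P1/P2 association of "change in GABA+/Cr between baseline and 16 weeks (post minus pre-treatment) and clinical improvement will be tested by regression". The listed covariates are age, sex, treatment group, MGH treatment resistance, "Baseline 17-item HDRS", study centre, MRS platform and "MRS quality (GABA+ fitting error"). The last is a quality measure, not a GABA level. The section on regions and voxels of interest adds grey matter: "The GM values will be covariates of no interest in the statistical analysis". The two sensitivity analyses concern voxel position and fit quality. Baseline GABA+/Cr appears in none of these places.

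The threshold is described as "5% significance level with Bonferroni correction for 3 co-primary hypotheses". S3 uses the same GABA+/Cr change and S7 uses Glx/Cr change; both are to be analysed in the same way as the primary hypotheses.

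**The concern.** The P1/P2 predictor is the 16-week level minus the baseline level, so a low baseline tends to produce a rise whenever levels move back toward the mean. P3 says that a low baseline also goes with improvement. The signs agree: one prognostic baseline effect pushes P1 and P2 in exactly the direction they predict, and the planned model cannot separate this from a link between change and outcome.

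This matters because the SAP gives its main rationale as whether response is associated with GABA change in the DLPFC, and its wider aim as understanding mechanism of action. A baseline marker could end up reported as two further co-primary findings about change. The SAP's own account of the pilot leaves both readings open: no GABA change at 3 months, some predictive power of baseline GABA (direction not stated), and a moderate correlation between the two changes.

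**Working it through.** **The plan's own figure.** 0.05/3 = 0.016667; the SAP prints 0.01666. This agrees. The SAP gives no sample size, power or effect size to reproduce.

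**Assumptions, since the SAP gives none.** Two-sided test; n = 60 or 100; correlation of baseline GABA+/Cr with improvement -r, with r = 0.3; scan-to-scan correlation ρ = 0.3 to 0.7; equal variances at the two scans; improvement scored so that positive is better. The SAP does not say which variable is dependent in P1/P2, but the partial test is the same either way.

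**Case 1: improvement depends only on the baseline level, which drifts toward its mean.** With unit variances, Var(change) = 2(1-ρ) and Cov(change, baseline) = ρ-1, so corr(change, baseline) = -√((1-ρ)/2). The induced correlation is

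corr(change, improvement) = r·√((1-ρ)/2).

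Approximate rejection rate in the predicted direction: P(Z > 2.394 - atanh(corr)·√(n-k-3)), where k is the degrees of freedom spent on other covariates. Example, n = 100, ρ = 0.5, k = 0: 0.3·√0.25 = 0.150; atanh = 0.1511; 0.1511 × √97 = 1.489; P(Z > 0.905) = 18.3%.

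| ρ | induced correlation | n=60, k=0 | n=60, k=10 | n=100, k=0 | n=100, k=10 |
|---|---|---|---|---|---|
| 0.3 | 0.177 | 14.9% | 12.2% | 26.5% | 23.6% |
| 0.5 | 0.150 | 10.5% | 8.7% | 18.3% | 16.2% |
| 0.7 | 0.116 | 6.5% | 5.5% | 10.7% | 9.6% |

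Simulation gives about 6–13% at n = 60 and 11–25% at n = 100, in line with the table. At ρ = 0.8 and n = 60 the rate is only 4.0%. P2 behaves like P1. With residual correlation 0.6 between the 16- and 26-week outcomes (assumed), both are significant together in 2.1–10.2% of runs at n = 100 (ρ = 0.8 to 0.4). With r = 0 the P1 rate is nominal, 1.4–1.5%.

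With baseline GABA+/Cr added, the change coefficient is the coefficient of the 16-week level given baseline. Here that is zero, and simulated P1 rejection returns to 1.3–2.2%.

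**Case 2: improvement depends on a stable trait and the scans differ only by measurement error.** Both scans then correlate -r with improvement, so change has covariance -r - (-r) = 0 with it. The planned model holds its level: 1.3–1.9% in simulation. The adjusted model does not. Solving the two-predictor equations gives a standardised change coefficient of -r/(1+ρ); at ρ = 0.5 this is -0.3/1.5 = -0.20, opposite to P1. At n = 100 and r = 0.3 it rejects in 7.8–31.9% of runs (ρ = 0.8 to 0.4), none of them in the P1 direction.

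**In between.** With scan reliability 0.6–0.8, n = 100 and the observed baseline correlation held at -0.3, the planned model rejects in the P1 direction in 13–14% of runs when true levels correlate 0.5 across scans, about 4% at 0.8, and about 1.3% at 0.95.

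**The case against.** The strongest reply is that the plan tests the hypothesis it states. P1 and P2 posit an association between two changes; if a baseline effect induces that association, P1 as worded is true. This stands. A reader might infer that the plan fails to control type I error, but Bonferroni is valid under dependence, and the P1 rate is nominal when baseline has no effect. A reader might also infer that the three co-primaries are claimed as independent findings; the SAP nowhere says so. What does not fall away is the step from association to mechanism, which the SAP's stated rationale invites.

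A second reply is that choosing between an unadjusted and a baseline-adjusted change model is a known judgement call. This also stands. Replacing the planned model with the adjusted one is tempting but not supported: Case 2 shows that noise in baseline GABA biases the adjusted coefficient against P1.

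Requiring significance in both models, and reading anything else as a P3 effect, is tempting too. It costs too much. In simulations where improvement was driven only by true GABA change (correlation 0.4, n = 100, reliability 0.6–0.8), detection fell from 58–83% to 34–65%, and 18–24% of runs would have been mislabelled as a baseline effect. Such a rule would even report a baseline effect when nothing was significant.

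**Conclusion.** The point holds as a limit on interpretation. Nothing in the planned P1/P2 analysis or the sensitivity analyses shows whether an association with GABA+/Cr change goes beyond the baseline effect that P3 itself posits. Under the assumed r = -0.3 and scan-to-scan correlation of 0.7 to 0.3, a baseline effect alone makes P1 significant in about 6–13% of trials at n = 60 and 11–25% at n = 100, against a nominal 1.67%. The rate depends on GABA drifting toward its mean, and it falls to about nominal if true GABA is stable and only the measurement varies. The SAP gives no figures that would place the trial within this range.

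S3 shares the GABA+/Cr problem. S7 has the same structure with Glx/Cr, but the SAP states no hypothesis about baseline Glx/Cr, so the figures above do not carry over to it.

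**What to change.** Keep the planned P1/P2 test and its 0.01667 threshold as primary. Pre-specify one supportive model each for P1, P2 and S3 that adds baseline GABA+/Cr, and for S7 one that adds baseline Glx/Cr. Report the change coefficient from both models side by side with confidence intervals.

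Add two sentences on reading the results:

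- A significant P1 or P2 whose change coefficient shrinks markedly or reverses after adjustment is not to be taken as clear evidence of a change mechanism, because a baseline (P3) effect cannot be excluded.
- Measurement error in baseline GABA+/Cr biases the adjusted coefficient against P1 when baseline level is prognostic, so attenuation alone does not prove a baseline effect either.

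No new data are needed, since everyone with a change score has a baseline value. The cost is one extra regression per hypothesis and a more cautious interpretation; the primary test loses no power.

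### Bonferroni at 0.05/3 for the three primary hypotheses is valid, but Holm's step-down test would confirm more at the same 5% family-wise error rate

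*SAP*

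**What the plan says.** The list of primary hypotheses in the SAP has three entries.

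- P1: "Changes in depression symptoms on 17-item HDRS (16 weeks versus baseline) will be associated with change in GABA+/Cr between baseline and 16 weeks".
- P2 uses the same GABA+/Cr change but takes the HDRS-17 change at 26 weeks.
- P3: "Greater clinical improvement on 17-item HDRS (16 and 26-week vs baseline) will be associated with lower GABA+/Cr at baseline across both treatment groups".

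Under Statistical tests, Primary Hypotheses, the threshold is 0.01666, explained as a "5% significance level with Bonferroni correction for 3 co-primary hypotheses". The threshold is the same for each hypothesis whatever the other two show. No step-down, gatekeeping or fixed-sequence rule is named.

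Under Secondary Hypotheses the SAP states: "For secondary analyses $P < 0.05$ will be considered significant without Bonferroni correction". The protected family is therefore P1-P3 and nothing else.

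**The concern.** Single-step Bonferroni holds every hypothesis to 0.05/3 even after another has been confirmed. Holm's procedure relaxes the threshold for the remaining hypotheses after each rejection, needs no further assumption, and keeps the same family-wise guarantee. Nothing in the SAP, such as a need for simultaneous confidence intervals, explains why the single-step form was chosen.

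The design is one in which a step-down rule can pay. P1 and P2 share a predictor and use the same scale ten weeks apart, so if one association is real the other plausibly is too. Together they are the direct tests of what the SAP calls its main rationale, that clinical response goes with GABA change. Confirming both would show that the association persists to 26 weeks. Under the present rule a true second or third association, with a p-value between 0.0167 and 0.025 or 0.05, would be reported as not significant although the 5% family-wise limit leaves room to confirm it.

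**Working it through.** **The plan's figure.** 0.05 / 3 = 0.016667. The SAP's 0.01666 is this value truncated. The sum over three tests is 3 × 0.016667 = 0.05. With independent tests the family-wise error rate (FWER) would be 1 − (1 − 0.016667)³ = 0.0492. The stated level reproduces and the control is sound.

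**The two rules.** Order the p-values p(1) ≤ p(2) ≤ p(3).

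- Bonferroni: reject each hypothesis with p < 0.05/3.
- Holm: compare p(1) with 0.05/3 = 0.0167, p(2) with 0.05/2 = 0.025 and p(3) with 0.05, stopping at the first failure.

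Every Holm threshold is at least 0.05/3, so Holm rejects everything that Bonferroni rejects. Both rules compare the smallest p-value with 0.0167, so the chance of at least one rejection is identical.

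**Example.** Take p = 0.010, 0.020, 0.040. Bonferroni confirms one hypothesis. Holm confirms three, because 0.010 < 0.0167, 0.020 < 0.025 and 0.040 < 0.05. The Holm-adjusted values are 3 × 0.010 = 0.030, 2 × 0.020 = 0.040 and 1 × 0.040 = 0.040.

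**Size under stated assumptions.** The SAP gives no sample size, effect size, power or sidedness. The inputs below are therefore assumptions: trivariate normal test statistics, two-sided tests, correlation 0.7 between P1 and P2 and 0.2 with P3, and the same power at 0.05/3 for each true hypothesis. Results are from simulation.

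| Truth | Power per test | Quantity | Bonferroni | Holm |
|---|---|---|---|---|
| All three true | 60% | each of P1, P2 | 60% | 68% |
| All three true | 60% | both P1 and P2 | 48% | 60% |
| All three true | 60% | all three | 32% | 50% |
| P1 and P2 true | 60% | each of P1, P2 | 60% | 63% |
| P1 and P2 true | 60% | both P1 and P2 | 48% | 54% |
| P1 and P2 true | 60% | false rejection of P3 | 1.7% | 3.6% |
| Only P1 true | 60% | P1 | 60.0% | 60.1% |
| All three true | 80% | per hypothesis | 80% | 87% |
| P1 and P2 true | 80% | false rejection of P3 | 1.7% | 4.2% |
| None true | – | any rejection (FWER) | 4.5% | 4.5% |

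**Other correlations.** The range ran from independent tests to 0.8 (P1-P2) with 0.5 (with P3). At 80% power per test:

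- all three true: average power rises to 86-88%, and power to confirm all three rises from 51-64% to 72-78%;
- two true: power per hypothesis rises to 82-83%;
- one true: the gain is about 0.1 point.

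Over assumed powers of 50% to 90%, Holm's FWER was at most 0.048 with one or two true nulls. Under the global null it was 0.041 to 0.049, the same as for Bonferroni.

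**The case against.** The strongest reply is that nothing is wrong here. The SAP names its family, chooses a valid correction and computes it correctly, and the same comment could be made of any plan that uses Bonferroni. That stands: the point concerns efficiency.

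A reader might go further and infer that the present rule buys nothing in return. That is not so. Bonferroni also caps the error rate of each single hypothesis at 1.67% and the expected number of false rejections at 0.05; Holm does not. When P1 and P2 are true, the rate for a null P3 roughly doubles in the table above, though it stays inside the 5% family-wise limit. Bonferroni also gives simple simultaneous confidence intervals.

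A reader might also infer that the study is likely to miss its main finding because of this rule. The SAP does not support that either. With no sample size or power given, the loss in this study cannot be quantified. The first success is no easier under Holm, and the background section describes the evidence on TMS and these metabolites as conflicting, so the case with all three hypotheses true should not be taken as expected.

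The word co-primary might suggest that all three must succeed, in which case no alpha split would be needed. The Bonferroni split shows that each hypothesis can be claimed on its own.

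Finally, Holm needs exactly one p-value per hypothesis. P3 is worded for 16 and 26 weeks, while its mixed model takes up to three repeated measures and no single contrast is named. Under Bonferroni that ambiguity stays within P3; under Holm it can shift the thresholds for P1 and P2. This objection stands and is answered in the fix.

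**Conclusion.** The point holds as an improvement. Single-step Bonferroni at 0.05/3 is valid; Holm offers the same 5% family-wise control under any dependence and never confirms fewer hypotheses. Under the assumed 60% power and 0.7/0.2 correlations, the gain is about 8 points per hypothesis if all three are true, 3 points if only P1 and P2 are true, and next to nothing if only one is true. The price is a higher error rate for an individual null hypothesis, within the family-wise limit, and less simple simultaneous intervals. The ordering of the two rules on the family-wise criterion needs no assumption; the sizes rest wholly on the assumed power, correlations and two-sided testing.

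**What to change.** Before results are seen, replace the significance sentence under Statistical tests, Primary Hypotheses with:

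> P1-P3 are tested by Holm's step-down procedure at a family-wise level of 5% (smallest p against 0.05/3, next against 0.05/2, largest against 0.05, stopping at the first failure), and Holm-adjusted p-values are reported. One pre-specified test of baseline GABA+/Cr from the P3 mixed model supplies the single p-value for P3.

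The SAP must then say which test that is: which visits enter it, and whether it is an effect averaged over visits or a contrast at one visit. It should also state whether the primary tests are one- or two-sided, since the hypotheses are worded directionally and no sidedness is given.

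The cost is a few sentences, with no new data, model or software. Ordinary confidence intervals can be reported beside the adjusted p-values, labelled as unadjusted.
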